1. PROTOCOL SUMMARY

Abbreviated Title	Pilot Study of Pembrolizumab and Single-fraction, Low-dose, Radiation Therapy in Patients with Relapsed or Refractory Multiple Myeloma
Trial Phase	Pilot Study
Clinical Indication	Relapsed or Refractory Multiple Myeloma
Trial Type	Pilot study
Type of control	None
Route of administration	Patients will receive on day 1, cycle 1 , radiotherapy (8 Gy/1fx) to an extra-osseous or osseous myeloma site followed by pembrolizumab (200 mg/kg i.v. on day 2 or 3 , then every 3 weeks +/- 7 days).
Trial Blinding	N/A
Number of trial subjects	24 patients (20 patients minimum, with 4 extra patients to account for loss to follow-up/attrition and/or failure to comply with recommended treatments); 12 patients will be allowed to not have measurable myeloma disease.
Estimated enrollment period	2 years
Description of enrollment	Following evaluation by medical oncology and radiation oncology, patients will be enrolled. Baseline assessment prior to enrollment may include bone marrow biopsy, peripheral blood collection, and staging of the patient per standard of care. Baseline serum and urine paraprotein analysis, bone marrow biopsy, PET/CT imaging, routine blood work, and baseline physical exam prior to enrollment. Patient with measurable myeloma disease will be screened for tolerability to Pembrolizumab and radiotherapy. Patients will be assessed at 1st month and every 3 month for response using the standard International Myeloma Working Group (IMWG) Response Criteria, and will undergo routine myeloma labs every 6 weeks until progression or as clinically indicated ; Patients with stable disease or better per IMWG response criteria will continue with maintenance pembrolizumab (200 mg/kg every 3 weeks for 2 yrs) . Patients that have progressive disease, or relapse after a complete response will be removed from the trial and treated per standard of care at the discretion of the treating physician.
Duration of Intervention	At least 24 months of Pembrolizumab, or until progression.
Duration of Evaluation	3 year (2 yrs for accrual, and at least 1 year follow-up for the last patient accrued on the study)
Estimated duration of trial	3 years (2 years to accrue + 1 years to follow all patients)
Duration of Participation	3 years
Study Center	Emory University. Atlanta, Georgia.

2. TRIAL DESIGN/SCHEMA

1. Trial Overview

Following evaluation by medical oncology and radiation oncology, patients with **measurable myeloma disease** will be enrolled. Baseline assessment prior to enrollment may include bone marrow biopsy, peripheral blood collection, and staging of the patient per standard of care. Baseline serum and urine paraprotein analysis, bone marrow biopsy, PET/CT imaging, skeletal survey, routine blood work, and baseline physical exam prior to enrollment. Patient will be screened for tolerability to Pembrolizumab, and those that are also eligible for radiotherapy will be identified.

Patients will receive on **day 1, cycle 1**, radiotherapy (**8 Gy/1fx**) to an extra-osseous site and/or any osseous bony site, followed by pembrolizumab (**200 mg/kg i.v. on day 2 or 3**). Baseline peripheral blood will be collected for myeloma response as well as for correlative biomarker analysis (timing of blood draws are defined in the flow chart in section 10.0).

Patients will be assessed for safety during routine visits, as well as treatment response using the standard International Myeloma Working Group (IMWG) Response Criteria (see Appendix II for IMWG Criteria) at **1 month** (shortly after completion of cycle 2 of pembrolizumab, anytime between **Day 23-30 +/- 7 days**), and **at least every 3 months +/-14 days (or as clinically indicated)**. Patients with stable disease or better per IMWG response criteria will continue with maintenance pembrolizumab (**200 mg/kg every 3 weeks for 2 yrs**). Patients that have progressive disease, or relapse after a complete response will be removed from the trial and will be treated per standard of care at the discretion of the treating physician.

Patients will continue to be monitored per standard of care on the trial. Patients will be monitored for known radiation related toxicity, known pembrolizumab toxicity, as well as any unexpected toxicity, per standard of care. PET/CT scans will be done at baseline and every 3 months, per standard of care.

The primary endpoint is to evaluate the **safety and tolerability** of concurrent single/low dose radiotherapy (8 Gy/1fx) in combination with pembrolizumab in relapsed and/or refractory myeloma patients at 3 months (**acute toxicity, primary endpoint**) and at 6 and 12 months (**late toxicity**). The secondary objective is to characterize the effect of radiation in combination with pembrolizumab on systemic response rates using international myeloma working group (IMWG) uniform response criteria for myeloma, to assess baseline changes in PET/CT as a result of combining pembrolizumab and radiotherapy, and to evaluate treatment response at irradiated and un-irradiated sites (i.e. the abscopal effect) using baseline PET/CT. Exploratory analysis would include analyzing Circulating Myeloma Tumor cells and phenotype of T cells as a prognostic and predictive biomarker. Compare blood Myeloma tumor cells with BM tumor cells. We are interested in comparing T cell phenotype after each treatment and using that as a prognostic biomarker. We will also evaluate serum LDH, CRP, ESR, ALC, cytokines and chemokines (such as IL-6, s IL-6R) and other immune related biomarkers, and correlate their expression pre and post treatment and evaluate changes in bone marrow biopsy and peripheral blood for mutational load, mutational signature (whole exome sequencing), transcriptome of the T cells, mutation specific T cells, PD1 and PDL1 expression on MM cells and T cells by flow/IHC, RNA-seq. Other biomarker correlative exploratory analysis (role of exosomes, etc) may also be pursued as ancillary research to this trial;

2. Acute Toxicity and Late Toxicity Assessment:

[figure not shown]
Acute toxicity (i.e. > Grade 2 CTCAE toxicity at **3 months**) associated with radiation therapy at the **radiated site** will be analyzed as the **primary safety endpoint** in this pilot study; Goal would be to see less than 20% > grade 2 toxicity at 3 months within the radiated area.

CTCAE criteria (see Appendix I) will be applied to assess acute toxicity.

Other endpoints that may be analyzed include late toxicity (> Grade 2 CTCAE toxicity at the radiated site at **6 months and 12 months**), systemic response against myeloma burden to localized radiation and pembrolizumab using IMWG uniform criteria, as well as other endpoints (defined in more detail in section 3.0).

3. Trial Schema

Figure 1: Trial Overview

Baseline work-up (per NCCN guideline) within 28 days +/- 14 days prior to enrollment: CBC with Diff, CMP, Calcium, Albumin, Serum Protein analysis, Quantitative Immunoglobulin, Serum Immunofixation (SIFE), 24 hr urine total protein, Urine Immunofixation, Serum Free Light Chain, Bone Marrow Biopsy (with IHC, flow, cytogenetics, FISH),

Whole Body PET/CT, Biopsy of Osseous or extra-osseous site (only if clinically indicated);
Pregnancy test;

Inclusion Criteria:

- 1) ≥ 18 years old; ISS stage I-III multiple myeloma that has progressive, relapsed, or refractory disease;
- 2) Able to give informed consent;
- 3) ECOG 0-1;
- 4) Relapsed and/or refractory myeloma; There is no minimum or maximum number of previous therapies that a patient may have received previously before being put on the current trial.
- 5) ≥ 1 osseous and/or extra-osseous lesion that can be radiated;
- 6) Candidate for pembrolizumab (as determined by physician, and adequate organ function as noted in **Table 1**);
- 7) Candidate for radiotherapy (as determined by treatment physician); These patients can have symptomatic disease and/or asymptomatic disease. A minimum of one site of radiation is required to any osseous and/or any extra-osseous disease. Radiation to any bony parts of the Head and Neck, Skull, Spine, ribs, and/or extremities are allowed. Radiation to any bony part for documented lytic disease is allowed. Radiation to any soft tissue plasmacytoma (including osseous and extra-osseous plasmacytoma) is allowed. The only exclusion criteria for radiation, is CNS metastases (see exclusion criteria # 16);
- 8) Measurable myeloma disease (**urine protein > 200 mg in 24 hr urine collection, serum free light chain ratio > 100 with an abnormal k/l ratio, serum M protein > 0.5 g/dl**) ; **12 of the 24 patients do not have to have measurable disease;**
- 9) Negative urine pregnancy test within 2 weeks for female subjects;

Female subjects of childbearing potential should have a negative urine or serum pregnancy within 72 hours prior to receiving the first dose of study medication. If the urine test is positive or cannot be confirmed as negative, a serum pregnancy test will be required.

- a. Female subjects of childbearing potential should be willing to use 2 methods of birth control or be surgically sterile, or abstain from heterosexual activity for the course of the study through 120 days after the last dose of study medication. Subjects of childbearing potential are those who have not been surgically sterilized or have not been free from menses for > 1 year.
- b. Male subjects should agree to use an adequate method of contraception starting with the first dose of study therapy through 120 days after the last dose of study therapy.

c. Abstinence is acceptable, if this is the usual life style and preferred contraception for the patient.

Exclusion Criteria:

- 1)** Previous anti-PD1 or anti-PD-L1;
- 2)** Solitary plasmacytoma;
- 3)** Smoldering (asymptomatic) multiple myeloma;
- 4)** Currently participating and receiving study therapy or has participated in a study of an investigational agent and received study therapy or used an investigational device within 4 weeks of the first dose of treatment;
- 5)** Has a diagnosis of immunodeficiency;
- 6)** Known history of active TB (Bacillus Tuberculosis);
- 7)** Hypersensitivity to Pembrolizumab or any of its recipients;
- 8)** Known additional malignancy that is progressing or requires active treatment (exceptions include basal cell carcinoma of the skin or squamous cell carcinoma of the skin);
- 9)** Has active autoimmune disease that has required systemic treatment in the past 2 years (i.e. with use of disease modifying agents, corticosteroids or immunosuppressive drugs);
- 10)** Known history of, or any evidence of active, non-infectious pneumonitis;
- 11)** Active infection requiring systemic therapy;
- 12)** Is pregnant or breastfeeding, or expecting to conceive or father children within the projected duration of the trial, starting with the pre-screening or screening visit through 120 days after the last dose of trial treatment.
- 13)** Has a known history of Human Immunodeficiency Virus (HIV) (HIV 1/2 antibodies).
- 14)** Has known active Hepatitis B (e.g., HBsAg reactive) or Hepatitis C (e.g., HCV RNA [qualitative] is detected).
- 15)** Has received a live vaccine within 30 days of planned start of study therapy.

Note: Seasonal influenza vaccines for injection are generally inactivated flu vaccines and are allowed; however intranasal influenza vaccines (e.g., Flu-Mist®) are live attenuated vaccines, and are not allowed.

16) Patients requiring radiation for CNS diseases are excluded (CNS defined as brain soft tissue/intra parenchymal metastases within the gray and white matter of the brain and/or for CSF disseminated disease, including leptomeningeal carcinomatous disease).

17) Has a history of Allogeneic Stem Cell Transplantation.

Follow-up:

Radiation Oncology: at 4 week post radiation and every 3 months (per standard of care, and as clinically indicated);

Medical Oncology: every 3 weeks, or as clinically indicated per standard of care for administration of pembrolizumab, and to monitor for any potential side effects from pembrolizumab;

Labs to be done during these visits:

Prior to cycle 2 of Pembrolizumab: Myeloma labs (CBC with diff, CMP, Calcium, Quantitative Immunoglobulin, M-Protein (Serum and Urine), Serum Free Light Chain);

Prior to Cycle 4 and every 6 weeks after that (until progression or as/clinically indicated): Myeloma labs (CBC with diff, CMP, Calcium, Quantitative Immunoglobulin, M-Protein (serum and Urine), Serum Free Light Chain);

Imaging: PET/CT will be done every 3 months;

Bone Marrow Biopsy: one biopsy at 6 months (if clinically indicated);

Table 1 - Adequate Organ Function Laboratory Values

System	Laboratory Value
Hematological	
Absolute neutrophil count (ANC)	$\geq 1,500 / \mu\text{L}$
Platelets	$\geq 75,000 / \mu\text{L}$ (rare exception for $\geq 50\text{K}$ per PI*)
Hemoglobin	$\geq 7.5 \text{ g/dL}$ or $\geq 5.6 \text{ mmol/L}$ and allow transfusion or EPO dependency (within 7 days of assessment)
Renal	
Serum creatinine OR Measured or calculated ^a creatinine clearance (GFR can also be used in place of creatinine or CrCl)	$\leq 1.5 \times$ upper limit of normal (ULN) OR $\geq 60 \text{ mL/min}$ for subject with creatinine levels $> 1.5 \times$ institutional ULN
Hepatic	
Serum total bilirubin	$\leq 1.5 \times$ ULN OR Direct bilirubin \leq ULN for subjects with total bilirubin levels $> 1.5 \times$ ULN
AST (SGOT) and ALT (SGPT)	$\leq 2.5 \times$ ULN OR $\leq 5 \times$ ULN for subjects with liver metastases
Albumin	$> 2.5 \text{ mg/dL}$
Coagulation	
International Normalized Ratio (INR) or Prothrombin Time (PT)	$\leq 1.5 \times$ ULN unless subject is receiving anticoagulant therapy as long as PT or PTT is within therapeutic range of intended use of anticoagulants
Activated Partial Thromboplastin Time (aPTT)	$\leq 1.5 \times$ ULN unless subject is receiving anticoagulant therapy as long as PT or PTT is within therapeutic range of intended use of anticoagulants
^a Creatinine clearance should be calculated per institutional standard.	

*In rare exceptions, where medical interest of patient to get on the trial supercedes the platelet cutoff, the PI can make an exception to allow a lab value lower than 75K. PI can allow for lab value up to 50K. * 50K cutoff is a lab value that used by several other myeloma protocols at Emory, especially for relapsed/refractory myeloma patients. The maximum number of patients that can be allowed this exception on the protocol is no more than 3. Transfusion is allowed to help increase platelets.

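### Two rows of Table 1 need correction: the hemoglobin limits printed in g/dL and mmol/L are not the same limit, and the albumin limit in mg/dL excludes nobody as written

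*Combined protocol and SAP*

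**What the plan says.** Inclusion criterion 6 in Section 2, repeated in Appendix VI, requires that the patient be a candidate for pembrolizumab in the physician's judgment and have "adequate organ function as noted in Table 1".

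Two rows of Table 1 matter here:

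- **Hemoglobin:** at least 7.5 g/dL or at least 5.6 mmol/L. The row goes on "and allow transfusion or EPO dependency (within 7 days of assessment".
- **Albumin:** above 2.5 mg/dL.

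No other section gives a hemoglobin or albumin limit, a conversion factor, or a reason for two hemoglobin limits. The only other serum protein threshold, in inclusion criterion 8, is in a different unit from albumin: "serum M protein > 0.5 g/dl".

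Two places deal with retreatment. The Second Course Phase text in Section 10 lists adequate organ function among its conditions. The paragraph in Section 7 on stopping treatment after a complete response refers to the safety parameters in the eligibility criteria. Neither names Table 1.

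**The concern.** A limit printed in two units should be one limit. If the two figures do not convert into each other, the row holds two cut-offs, and a reader cannot tell which was meant. A limit in the wrong unit is a separate fault: it can look like a screen and yet be met by every patient.

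These are decision thresholds for entry to a trial whose primary objective is safety. What is at stake is whether eligibility can be applied and audited from the text alone. The estimates that the trial will report are not at stake.

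**Working it through.** **Inputs from Table 1.** Hemoglobin 7.5 g/dL and 5.6 mmol/L; albumin 2.5 mg/dL.

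**Assumption.** The documents give no hemoglobin conversion. I use the standard monomer basis, with molar mass M about 16,114 g/mol and a range of 16,000 to 16,125:

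factor (mmol/L per g/dL) = 10 × 1000 / M

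This gives 10,000 / 16,114 = 0.6206, with a range of 0.620 to 0.625.

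**Hemoglobin: do the two printed values agree?**

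| Factor | 7.5 g/dL in mmol/L | 5.6 mmol/L in g/dL | Gap in g/dL |
|---|---|---|---|
| 0.620 | 7.5 × 0.620 = 4.65 | 5.6 / 0.620 = 9.03 | 1.53 |
| 0.6206 | 7.5 × 0.6206 = 4.65 | 5.6 / 0.6206 = 9.02 | 1.52 |
| 0.625 | 7.5 × 0.625 = 4.69 | 5.6 / 0.625 = 8.96 | 1.46 |

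The printed pair is not reproduced at any factor in the range.

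**Could rounding explain it?** If 5.6 stands for anything from 5.55 to 5.65, then at 0.6206 the equivalents are 5.55 / 0.6206 = 8.94 and 5.65 / 0.6206 = 9.10 g/dL. The gap is 1.44 to 1.60 g/dL, so rounding does not close it.

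**Could another conversion explain it?** The pair would agree only at a factor of 5.6 / 7.5 = 0.747, which implies M = 10,000 / 0.747, or about 13,390 g/mol, outside the assumed range. The tetramer basis (M = 64,458, factor 0.155) turns 5.6 mmol/L into about 36 g/dL, which is further away.

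**Could two cut-offs be intended?** The platelet row of the same table does carry two, 75,000 and 50,000 per µL. There the table marks the lower one as an exception, and a footnote explains it and caps it at 3 patients. The hemoglobin row has no such note.

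**Effect of the hemoglobin row under each reading.**

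- *'Or' taken literally:* meeting either value is enough. Anyone at or above about 9.0 g/dL already meets 7.5 g/dL, so the mmol/L figure has no effect.
- *The mmol/L figure used alone:* patients from 7.5 up to about 9.0 g/dL are excluded, although they meet the g/dL figure.

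**Albumin.** 2.5 mg/dL = 2.5 / 1000 = 0.0025 g/dL, a thousandth of the same number in g/dL. Take 0.5 g/dL as a deliberately low illustrative value: it is 500 mg/dL, and 500 / 2.5 = 200 times the printed limit. The criterion therefore excludes nobody in practice.

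**The case against.** The strongest reply is that little follows in practice. The parts of it fare differently.

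- **The 'or' settles the hemoglobin row.** Taken literally it does: a patient at 8 g/dL is eligible. A reader might infer that such patients are bound to be judged eligible or ineligible according to the unit reported. The documents do not support that, because it happens only if someone applies the mmol/L figure alone. The row remains inconsistent, since one of its two values is then redundant.
- **Only one study center is listed, in Atlanta, Georgia.** Nothing in the documents shows that its laboratory will report hemoglobin in mmol/L. This makes inconsistent hemoglobin screening unlikely. It has no bearing on albumin.
- **Table 1 is not the only screen.** Criterion 6 also requires a physician's judgment, and the hemoglobin row accepts transfusion or EPO support. A reader might infer that patients with low albumin enter with no protection at all. That goes too far: a screener would probably notice the implausible unit and query it. But eligibility would then rest on an unwritten correction, and an auditor applying the text would find no effective albumin criterion.
- **Retreatment is not clearly governed by the table.** A reader might infer that Table 1 controls entry to the Second Course. The link is plausible but indirect, because neither relevant section names the table.
- **The table was read from a PDF by a program.** Both rows are complete and legible, with no sign of redaction. A check against the source document would settle any doubt.

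**Conclusion.** Both rows need correction. The two hemoglobin values are different limits, about 1.5 g/dL apart (1.4 to 1.6 allowing for rounding of 5.6). That figure rests on the assumed monomer conversion of 0.620 to 0.625. The pair is inconsistent, but this does not show that either value alone is wrong, and the documents do not settle which was intended.

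The albumin limit has no effect as written. A unit error is the probable cause, because the protocol's other serum protein limit is in g/dl, but the sponsor must confirm this. The albumin result needs no outside conversion factor.

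The Second Course may be affected as well, through its own reference to organ function and the Section 7 reference to the eligibility criteria.

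Severity is low. The primary endpoint, sample size, confidence intervals and analysis sets do not depend on either row.

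**What to change.** The sponsor should:

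1. Reconcile the two hemoglobin values to a single limit, or print the limit in one unit only.
2. Confirm the intended albumin limit and correct its unit.
3. If Table 1 is meant to apply at retreatment, name it in the Second Course conditions in Section 10.

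This review does not say which hemoglobin or albumin limit is right. The first two changes touch two cells of Table 1, and the third adds a cross-reference. None of them affects the design or the analysis. Appendix VI refers back to Table 1 and does not repeat its limits, so it needs no separate edit for these rows.

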3. OBJECTIVES, ENDPOINTS & HYPOTHESES

1. Primary Objective, Endpoint, & Hypothesis

Primary Objective

To evaluate the safety of concurrent single/low dose radiotherapy (**8 Gy/1fx**) in combination with Pembrolizumab in relapsed or refractory myeloma patients; **Once 10 patients are enrolled, we will stop trial for 3 months to assess for acute toxicity, and then resume the trial.**

Primary Endpoint

CTCAE > grade 2 toxicity at the specific irradiated **organ site at 3 months** (the Dose Limiting Toxicity);

Primary Hypothesis

The primary hypothesis of this pilot study is that the use of concomitant Pembrolizumab and radiation therapy in multiple myeloma patients will be well tolerated and safe.

Alternative Hypothesis

It is possible that concurrent use of radiotherapy and Pembrolizumab in relapsed/refractory myeloma may increase CTCAE > grade 2 toxicity within the radiated site at 3 months.

2. Secondary Objective(s), Endpoint(s) & Hypothesis (es)

Secondary Objectives

To characterize late toxicity (CTCAE > grade 2 toxicity at **6 and 12 months**) and the effect of radiation in combination with Pembrolizumab on systemic response rates using international myeloma working group (IMWG) uniform response criteria for multiple myeloma at **6 months and 12 months**;

To assess changes in PET/CT as a result of combining Pembrolizumab and radiotherapy at **6 months and 12 months**;

Secondary Endpoints

- a. 1. Number of patients achieving any response (from baseline) per IMWG response criteria at **6 months and 12 months**;
- b. 2. Overall survival time at **6 months and 12 months**;
- c. 3. Overall response based on baseline changes on PET/CT at **6 months and 12 months**;
- d. 4. Difference in pre and post treatment serum immune biomarkers;

Secondary Endpoint Definitions

- a. Response is defined per IMWG criteria, and will be calculated at **6 months and 12 months**;
- b. Overall survival will be defined as time from first treatment on cycle 1, day 1 to the earlier of date of death and/or last follow up at **6 months and 12 months**.
- c. Overall response will be defined using IMWG uniform response criteria.
- d. Several serum biomarkers will be analyzed.

Secondary Hypotheses

The secondary hypothesis is that low dose/single fraction (8Gy/1fx) will synergize with Pembrolizumab for a more effective anti-myeloma response per IMWG, via the radiation induced abscopal response.

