11. STATISTICAL ANALYSIS PLAN

1. Statistical Analysis Plan Summary

Study Design

The study is a pilot study to look at the safety of concurrent PD-1 inhibitor and SRS for relapsed/refractory myeloma. A total of 24 patients will be enrolled on the trial (20 is the minimum, with an additional 4 patients, to make for any attrition and/or loss to follow-up). 12 patients will be allowed to not have measurable myeloma disease in this trial. Once 10 patients are enrolled, we will stop trial for 3 months to assess for acute toxicity, and then resume the trial. The estimated exact Clopper-Pearson 95% confidence interval for a 20% rate based on 5 responses in 20 patients is (0.087, 0.491), with a precision of 0.185. If we see lower than 20% difference in rate of toxicity at 3 months, the combination will be deemed safe.

A minimum of 20 patients are required to complete full treatments. An additional 20% is allowed for drop out/failure to adhere to required follow-up and treatment recommendations. Thus, 24 patients will be allowed to be enrolled on the trial to make for any attrition and/or loss to follow-up. 12 patients will be allowed to not have measurable myeloma disease.

# of Responses / # of Patients	95% confidence interval
5 / 20	(0.087, 0.491)
6 / 24	(0.098, 0.467)

Populations for analysis

- Enrolled set: All subjects who signed an informed consent.
- Safety set: All subjects who received at least one dose of any study drug.
- Full analysis set: All subjects from the safety set who have the required follow-up and treatment adherence to evaluate response and safety over time.

2. Statistical Analyses

1. Response

IMWG criteria will be used to assess response. Proportion of patients achieving stable

disease or better will be reported at **6 months** and **12 months**; Response rates will be reported along with 95% confidence intervals will be estimated using the Clopper-Pearson method.

2. Safety

Proportion of acute (at **3 months**) and late toxicity (**6 and 12 months**) will be reported, and 95% confidence intervals will be estimated using the Clopper-Pearson method.

3. Overall Survival

For overall survival, death from any cause will be defined as the event. Patients will be censored at time of last follow-up. OS will be estimated using the Kaplan-Meier product-limit method. Overall survival will be analyzed at **6 months, and 12 months**.

4. Biological variables

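### The PET/CT response endpoint is defined by IMWG criteria, so it repeats the IMWG endpoint and leaves the PET/CT objective without a definition or an analysis

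*Combined protocol and SAP*

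**What the plan says.** Section 3.2 gives four lettered secondary endpoints and four lettered definitions.

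- Endpoint (a): "Number of patients achieving any response (from baseline) per IMWG response criteria at" 6 and 12 months. Definition (a): "Response is defined per IMWG criteria, and will be calculated at" the same two times.
- Endpoint (c): "Overall response based on baseline changes on PET/CT at" 6 and 12 months. Definition (c): "Overall response will be defined using IMWG uniform response criteria".

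PET/CT change is also an objective in its own right in Section 3.2: "To assess changes in PET/CT as a result of combining Pembrolizumab and radiotherapy at" 6 and 12 months. Section 2 states its purpose, which is to "evaluate treatment response at irradiated and un-irradiated sites (i.e. the abscopal effect) using baseline PET/CT".

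The Response paragraph of Section 11 opens with "IMWG criteria will be used to assess response". It then plans the proportion with stable disease or better at 6 and 12 months, with exact 95% intervals. The other analyses listed are safety, overall survival and biological variables.

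Inclusion criterion 8 in Section 2 defines measurable disease by urine protein, serum free light chains and serum M protein. It exempts 12 of the 24 patients from having it.

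**The concern.** An endpoint and its definition should describe the same measurement. Here the endpoint is an imaging change, and the definition points to the criteria already used for another endpoint. This is a wrong stated rule, not just a missing detail: an analyst who follows it produces the IMWG result twice and no PET/CT result.

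The secondary hypothesis in Section 3.2 is that radiation strengthens the systemic response through an abscopal effect. PET/CT is the tool that Section 2 names for looking at sites inside and outside the radiation field. Without a lesion-level rule, the trial collects the scans but has no planned way to address that question. An analyst who sees the gap late could choose among several criteria named elsewhere in the protocol after seeing the data.

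**Working it through.** The plan gives no figure for this endpoint, so the check is textual.

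**Step 1. Match endpoints to definitions (Section 3.2).**

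| Item | Endpoint | Definition | Times |
|---|---|---|---|
| (a) | Any response per IMWG | IMWG | 6 and 12 months |
| (c) | Response from PET/CT change | IMWG | 6 and 12 months |

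The definition column is the same in both rows. No uptake measure, lesion count, size rule or cutoff is attached to (c).

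**Step 2. Look for the missing rule in Section 11.** Of the four analyses listed, the only one on response is by IMWG. None uses PET/CT, and none separates irradiated from un-irradiated lesions.

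**Step 3. Look for it elsewhere.**

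- Section 14.1 (Data Collection) records PET/CT under RECIST.
- Appendix II is RECIST 1.1, although the Trial Overview in Section 2 sends the reader to Appendix II for IMWG. The IMWG criteria are in Appendix IV, as a heading and a web link only.
- Appendix III sets out immune-related response criteria (irRC) and says that these underlie the key efficacy endpoints. They rest on lesion diameters and class bone lesions as non-measurable, whereas Section 2 enrolls patients for irradiation of osseous or extra-osseous lesions. Lesions in previously irradiated areas are also non-measurable, without saying whether that covers the lesion treated on day 1.

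Three sets of criteria (IMWG, RECIST, irRC) therefore compete for the term overall response. None is a PET/CT rule that separates sites inside and outside the field.

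**Step 4. Patients without measurable disease.** Criterion 8 allows 12 of 24, or 12/24 = 50%. Sections 3 and 11 and the appendices do not say how response is scored in these patients, or whether they count in the denominator.

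**Step 5. Who could be evaluated on PET/CT.** The documents do not allow a count.

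- Section 2 requires at least one lesion that can be irradiated, and Section 8 accepts evidence from X-ray, CT, PET/CT or MRI. A patient may therefore have no avid lesion, or none outside the field.
- The flow chart footnote in Section 9.1 makes the three-monthly PET/CT subject to insurance approval.
- Section 2 removes patients with progression from the trial, and Section 10 is not consistent on whether imaging continues after progression. Scans at 6 and 12 months may therefore be missing selectively.

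**The case against.** The strongest reply is that this is one descriptive secondary endpoint in a single-arm safety pilot, that the intention is clear from Section 2, and that imaging criteria do exist in the protocol. Part of this stands. The primary endpoint and enrollment are unaffected, and the aim of looking at irradiated and un-irradiated sites is stated. What is missing is the operational rule, and the criteria named elsewhere contradict definition (c) and each other.

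Three stronger readings are tempting, and the documents do not support them.

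- A reader might infer that patients without measurable disease cannot be scored for response at all. Criterion 8 governs eligibility, and the IMWG rules are only linked, so whether they allow scoring by other means cannot be checked here. For the same reason, endpoint (a) cannot be called purely serologic.
- A reader might then put a price on it: for a 25% rate, the exact 95% interval widens from 9.8–46.7% (6/24, as in the table in Section 11) to 5.5–57.2% (3/12). The arithmetic is right, but it assumes that all 12 places are used and that none of those patients can be scored. It also describes endpoint (a), whose precision a PET/CT definition would not restore.
- A reader might infer that the PET/CT scans go unused. Section 14.1 captures them, and radiographic progression enters the withdrawal and follow-up rules in Sections 7 and 10. What is absent is the planned secondary analysis.

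**Conclusion.** The point holds. Definition (c) assigns IMWG criteria to a PET/CT endpoint, and Section 11 supplies no PET/CT analysis. Under the plan as written, one of the four listed secondary endpoints duplicates another, and the PET/CT objective and the abscopal comparison go unanswered. Separately, up to half of the patients (12 of 24, a ceiling and not a forecast) have no stated scoring or denominator rule for response.

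The conclusion rests on the text alone and needs no assumption about the content of the IMWG criteria. No loss of precision can be given for endpoint (c), because the number of patients evaluable on PET/CT is unknown. The change should be made, but it does not touch the primary safety result.

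**What to change.** 1. Replace definition (c) in Section 3.2 with a single prespecified PET/CT definition that includes a response cutoff. It could use, for example, percent change from baseline in uptake and the number of avid lesions, at 6 and 12 months, in patients with at least one avid baseline lesion. Without a cutoff there is no proportion to report.
2. Report irradiated lesions separately, and base the systemic PET/CT response on un-irradiated lesions only, so that the direct effect of 8 Gy is not counted as systemic. The denominator for that part is then patients with at least one un-irradiated avid lesion at baseline.
3. Reconcile Section 14.1 and Appendices II and III with the new definition, and correct the appendix reference for IMWG in Section 2.
4. Add a line to Section 11 giving the proportion with its Clopper-Pearson 95% interval and the median percent change. State the denominator and how scans are handled when they are missing through lack of insurance approval or after progression.
5. State in Section 11 how IMWG response is scored in patients without measurable disease, and whether they are in the denominator.

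The cost is an amendment to the endpoint and analysis wording, plus more lesion-level recording per scan. No new visits or scans are needed.
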